9.2 Documenting and Reporting of Adverse Events (Including Serious Adverse Events)

Adverse events will be evaluated and documented using the grading scales contained in the National Cancer Institute Common Terminology Criteria for Adverse Events (NCI-CTCAE) Version 5.

9.2.1 Documenting and Reporting Adverse Events

All AEs reported from the time of informed consent to the EOS visit for each subject will be recorded in the subject's source documents. For subjects who do not receive study drug (ie, alternates or screen failures), AEs will only be recorded in the source documents. For subjects enrolled into the study (ie, randomized), all AEs will be recorded in the subject's AE eCRF and the SAE form (if applicable). The site should record all AEs regardless of the intensity, seriousness, or relationship to study drug.

Adverse events (serious and nonserious) will be graded in accordance with the NCI-CTCAE scale as follows:

- **Mild** (Grade 1): asymptomatic or mild symptoms; clinical or diagnostic observations only; intervention not indicated
- **Moderate** (Grade 2): minimal, local or noninvasive intervention indicated; limiting age-appropriate instrumental activities of daily living

- **Severe** (Grade 3): severe or medically significant but not immediately life-threatening; hospitalization or prolongation of hospitalization indicated; disabling; limiting self-care activities of daily living
- **Life threatening** (Grade 4): life-threatening consequences; urgent intervention indicated
- **Death** (Grade 5): death related to the AE

Any recurrence of an AE with similar causality to study drug will be reported as recurrence or exacerbation of the initial event, and not as a new event. Whenever possible, AEs will be reported as a specific diagnosis or syndrome (eg, flu syndrome) rather than as individual signs or symptoms. If no specific diagnosis or syndrome is identified, AEs should be reported as separate and individual events.

An AE includes the following:

- Progression or exacerbation of the subject's underlying disease. Clinical sequelae that result from disease progression, such as pleural effusion or small bowel obstruction, are reportable as AEs
- Pre-existing event that increases in frequency or intensity
- Condition detected or diagnosed during the study period, even though it may have been present, in retrospect, before the first dose of study drug
- Laboratory abnormalities outside of normal limits with associated clinical symptoms or suspected latent clinical symptoms in the opinion of the Investigator, including those requiring therapeutic intervention

The following events will not be identified as AEs in this study:

- Medical or surgical procedures (eg, surgery, endoscopy, tooth extraction, etc); however, the condition (the "triggering event") that leads to the procedure may be an AE
- Pre-existing conditions present or detected before the first dose of study drug that do not worsen

9.2.2 Assigning Attribution of Adverse Events

The Investigator must attempt to determine the cause of each event. Every effort will be made by the Investigator to assess the relationship of each AE to study drug. To ensure consistency of AE/SAE causality assessments, the Investigator should apply the following guidelines:

- **Related:** There is an association between the event and the administration of study drug, a plausible mechanism for the event to be related to the study drug and causes other than the study drug have been ruled out, and/or the event reappeared on re-exposure to the study drug.

- **Possibly related:** There is an association between the event and the administration of the study drug and there is a plausible mechanism for the event to be related to study drug, but there may also be alternative etiology, such as characteristics of the subject's clinical status or underlying disease.
- **Unlikely related:** The event is unlikely to be related to the study drug and likely to be related to factors other than study drug.
- **Not related:** The event is related to an etiology other than the study drug (the alternative etiology must be documented in the study subject's medical record).

9.2.3 Classifying Action Taken With Study Drug

In the case of an AE, the actions that can be taken with study drug by the Investigator or designee are defined in [Table 2](#).

Table 2: Options for Action Taken With Study Drug

Classification	Definition
Dose not changed	Study drug dose not changed in response to the adverse event.
Drug interrupted	Study drug administration interrupted in response to an adverse event.
Drug withdrawn	Study drug administration permanently discontinued in response to an adverse event.
Not applicable	Action taken regarding study drug administration does not apply. "Not applicable" should be used in circumstances when no opportunity to decide whether to continue, interrupt, or withdraw treatment was possible such as when the investigational treatment had been completed before the adverse event began.

9.2.4 Classifying Adverse Event Outcome

For every AE/SAE, the possible outcomes of the event and the definition of the outcome are shown in [Table 3](#). One outcome must be entered into the appropriate field on the AE and (if appropriate) SAE form for each event.

Table 3: Classification and Definition of Adverse Event Outcomes

Classification	Definition
Recovered/resolved	Resolution of an adverse event with no residual signs or symptoms
Recovered/resolved with sequelae	Resolution of an adverse event with residual signs or symptoms
Is Recovering/is resolving	Incomplete improvement to date but adverse event continues to improve/resolve and complete resolution is expected over time
Not Recovered/not resolved	Either incomplete improvement or no improvement of an adverse event, such that it remains ongoing
Fatal	Outcome of an adverse event is death. "Fatal" should be used when death is at least possibly related to the adverse event
Unknown	Outcome of an adverse event is not known (eg, a subject lost to follow-up)

9.2.5 Documenting and Reporting Serious Pretreatment Events and Serious Adverse Events

All SAEs that occur after obtaining informed consent through the EOS visit, regardless of causality, must be reported by the Investigator or designee to [REDACTED] and Enanta Pharmaceuticals, Inc. In addition, all SAEs, including those that result in death, that occur after the EOS visit and that are considered related to study drug must be reported to [REDACTED] and Enanta Pharmaceuticals, Inc. within 24 hours of learning of its occurrence. Additional details are provided in the Safety Management Plan. The SAE form should be sent to [REDACTED].

Serious Adverse Event and Pregnancy Reporting

[REDACTED] Email at [REDACTED]

[REDACTED] Faxed to [REDACTED]

[REDACTED] Phone contact is [REDACTED]

All SAEs will be recorded on the SAE form using a recognized medical term or diagnosis that accurately reflects the event. All SAEs will be assessed by the Investigator for severity, relationship to the investigational study drug, and possible etiologies. On the SAE form, relationship to study drug will be assessed only as related or not related. For the purposes of study analysis, if the event has not resolved at the end of the study reporting period, it will be documented as ongoing.

For purposes of regulatory safety monitoring, the Investigator is required to follow up the event to resolution and report the outcome of the event to [REDACTED]
[REDACTED], and Enanta Pharmaceuticals, Inc. using the SAE form.

The Investigator or designee is responsible for notifying the Sponsor within 24 hours of identifying an SAE, regardless of the presumed relationship to the investigational study drug. The SAE form should be completed for new/initial events as well as to report follow-up information on previously reported events. The Investigator or designee is asked to report follow-up information as it becomes available.

Enanta Pharmaceuticals, Inc. or its designee, as study Sponsor, is responsible for reporting suspected, unexpected, serious adverse reactions (ie, SUSARs) involving the study drug to all regulatory authorities, and participating investigators, in accordance with United States Food and Drug Administration (FDA), International Council for Harmonisation of Technical Requirements for Pharmaceuticals for Human Use (ICH) guidelines, and/or local regulatory requirements, as applicable.

9.2.6 Documenting and Reporting of Pregnancy

Subjects will be counseled to inform the Investigator of any pregnancy that occurs during study drug and for 90 days after the last dose of study drug.

If a female subject or the female partner of a male subject becomes pregnant while participating in the study, study drug must be permanently discontinued immediately. The Investigator or designee must notify [REDACTED] (Section 9.2.5), the Sponsor's Medical Monitor, and [REDACTED] within 1 business day of the sites' knowledge of the subject's (or partner's) pregnancy, by utilizing the study-specified pregnancy report form.

If confirmed to be on active drug, the subject or partner will be followed up until the end of the pregnancy and the infant will be followed up for 3 months after the birth, provided informed consent is obtained. A separate ICF will be provided to explain these follow-up activities. Pregnancy itself does not constitute an AE.

9.3 Follow-up of Adverse Events and Serious Adverse Events

All AEs (serious and nonserious) will be followed up until resolution or otherwise explained (see Table 3), the subject dies, the event stabilizes and is not expected to further resolve with the maximum time limit for stabilization defined as 30 days after the occurrence of the event, or when alternative therapy is instituted, whichever occurs first. If alternative therapy is instituted, it should be documented. Enanta Pharmaceuticals, Inc. may request that the Investigator perform or arrange for supplemental measurements or evaluations to further clarify the nature of the event.

9.4 Data Monitoring Committee

Safety data from this study will be reviewed by a DMC throughout the study. The DMC will be headed by a DMC Chair and will include one or more physicians with expertise in transplant medicine, consisting of expert(s) independent from the Sponsor. Procedures for data review, including timing and potential outcomes, roles and responsibilities, and interactions with the Sponsor and PPD, will be governed by a separate DMC charter.

10. STUDY STOPPING AND DISCONTINUATION RULES

10.1 Study Stopping Rules

If either of the following events occur, enrollment will be paused pending a full review of all available clinical safety data and discussion with the DMC:

- One subject has a Grade 4 AE or SAE that is judged as possibly related to study drug
- Two subjects experience the same Grade 3 AE that is judged as possibly related to study drug

Unless the subject's randomization code is unblinded by the Sponsor for clinical reasons, only the DMC will have access to unblinded data.

10.2 Site or Study Discontinuation

10.2.1 Study Discontinuation

The Sponsor has the right to terminate this study at any time. Reasons for terminating the study may include, but are not limited to, the following:

- Incidence or severity of AEs in this study indicates a potential health hazard to subjects
- Subject enrollment is unsatisfactory
- Data recording is inaccurate or incomplete
- Investigator does not adhere to the protocol or applicable regulatory guidelines in conducting the study
- Decision from the IRB/EC or regulatory authority to terminate the study

If the study is suspended or terminated for safety reasons, Enanta Pharmaceuticals, Inc. will promptly notify the investigators and will also inform the regulatory authorities of the suspension or termination of the study and the reasons for the action. The Investigator is responsible for promptly informing the IRB/EC and providing the reasons for the suspension or termination of the study.

10.2.2 Site Termination

A single site may warrant termination under the following conditions:

- Failure of the site to enroll subjects into the study at an acceptable rate
- Failure of the site to comply with pertinent governmental regulations as appropriate

- Submission of knowingly false information from the research facility to the Sponsor, Clinical Monitor, or governmental authority
- Failure to adhere to the protocol requirements
- Data recording is inaccurate or incomplete
- Investigator does not adhere to the protocol or applicable regulatory guidelines in conducting the study

10.2.3 Study Termination Procedures

If the study is terminated by Enanta Pharmaceuticals, Inc. for one of the reasons listed previously, or upon completion of the study, the following activities must be conducted by the Study Monitor and/or site staff:

- Return of all study data to Enanta Pharmaceuticals, Inc. or designee
- Respond to and complete all requests for data clarifications
- Accountability and final disposition of used and unused study drug
- Review of site records for completeness
- Shipment of all applicable biological samples (including PK samples) to the designated laboratory

11. STATISTICAL CONSIDERATIONS

11.1 General Considerations

Statistical analysis of this study will be the responsibility of Enanta Pharmaceuticals, Inc. or its designee. Details of the statistical analysis methods will be described in the statistical analysis plan (SAP) document.

Continuous endpoints will be summarized using n, mean, standard deviation, median, 25th quartile, 75th quartile, minimum, and maximum values. Categorical endpoints will be summarized by the number of subjects meeting the endpoint and the percentage of subjects out of the appropriate population. The denominator will be displayed when needed. Statistical inference will be performed as appropriate. Inferential testing will be conducted using a two-sided alpha of 0.05, unless stated otherwise. Reference to stratification factors will include ribavirin treatment (presence or absence) and ALC (<200 or \geq 200 cells/ μ L) at Screening.

Any change to the data analysis methods described in the protocol will require an amendment if it changes a principal feature of the protocol. Any other change to the data analysis methods described in the protocol, and the justification for making the change, will be described in the CSR or SAP. The SAP will be developed and finalized before database lock. Changes to the SAP may not be made after unblinding of treatment assignments (after database lock).

11.2 Sample Size Considerations

Assuming an LRTC rate of 30% for placebo, then a 20% reduction with 90% power and a two-sided alpha at 0.05 using a unpooled z-test, with a ratio of 2:1 would require approximately 160 subjects. Assuming a 15% dropout rate a total of 190 subjects will be randomized.

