Subject Eligibility Criteria: Males and females aged between 16 and 75 years, inclusive, who have received an autologous HCT (within 6 months of signing ICF) and have an ALC <300 cells/ μ L OR received an allogeneic HCT (any time) and have an ALC <500 cells/ μ L,

and are diagnosed with RSV with new onset of respiratory symptom(s). This includes subjects who have oxygen saturation $\geq 95\%$ on room air and body mass index (BMI) up to 40 kg/m^2 .

Subjects with new abnormalities consistent with LRTI on chest imaging, hospital admission for a lower respiratory tract disease of any cause, positive for other respiratory viruses or having clinically significant viremia, bacteremia, or fungemia will be excluded from the study. Also excluded are subjects with known heart, liver, or kidney disease, or any historical or current medical condition that, in the opinion of the Investigator, deems the subject unsuitable for the study.

Statistical Methods: Detailed statistical analysis will be outlined in the statistical analysis plan, which will be developed and finalized before database lock.

Sample Size Considerations: Assuming an LRTC rate of 30% for placebo, then a 20% reduction with 90% power and a two-sided alpha at 0.05 using a unpooled z-test, with a ratio of 2:1 would require approximately 160 subjects. Assuming a 15% dropout rate a total of 190 subjects will be randomized.

Statistical Analysis: The following analysis populations are planned:

Intent-to-Treat (ITT) Population: All subjects who receive at least one dose of study drug. Subjects will be analyzed as treated. The ITT Population is designated as the primary efficacy population.

Per Protocol Population: All subjects who are randomized and receive all planned doses of study drug and do not have major protocol deviations that may unduly influence outcome. Subjects will be analyzed in the treatment group that corresponds to the study drug received during the study.

Safety (SAF) Population: All subjects who receive at least one dose of study drug. Subjects will be analyzed in the treatment group that corresponds to the study drug received during the study.

Pharmacokinetic (PK) Population: All subjects receiving active study drug and having any measurable plasma concentration of study drug at any timepoint.

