3. SELECTION OF SUBJECTS

A total of approximately 200 subjects are planned to be enrolled into this study.

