5.6 Treatment Assignment/Randomization

Subjects will be randomized to a treatment group using an Interactive Web Response System (IWRS). Subjects will be randomized in a 2:1 ratio to the EDP-938 or placebo treatment group as shown below:

- Treatment Group 1 (approximately 130 subjects): either [REDACTED] (see Section 4.1) of EDP-938 orally QD for 21 days
- Treatment Group 2 (approximately 70 subjects): Placebo orally QD for 21 days

In addition, subject randomization will be stratified based on ribavirin treatment (presence or absence) and ALC (<200 or \geq 200 cells/ μ L) at Screening.

During the Screening Period, subjects will be identified by a unique screening number assigned by the clinical site. Subjects who have completed screening assessments and are eligible for participation in the study will be randomized before the first dose of study drug (Day 1) and assigned a unique four-digit subject number that will be used to identify the subject throughout the study.

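### The protocol's 160 evaluable subjects at 2:1 give about 82% power by the stated unpooled z-test, not 90%, and the randomised total is 190 in some places and about 200 in others

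*Protocol*

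**What the plan says.** Protocol Section 11.2 and the matching synopsis paragraph give every input to the calculation. The control rate is set by "Assuming an LRTC rate of 30% for placebo". The effect and error rates follow: "then a 20% reduction with 90% power and a two-sided alpha at 0.05". The method, ratio and answer are "with 90% power and a two-sided alpha at 0.05 using a unpooled z-test, with a ratio of 2:1 would require approximately 160 subjects". The dropout step is "Assuming a 15% dropout rate a total of 190 subjects will be randomized".

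Section 5.6 fixes the direction of the ratio as two EDP-938 subjects to one placebo subject.

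The total appears differently elsewhere. Section 3 says "A total of approximately 200 subjects are planned to be enrolled into this study", and the synopsis line on the number of subjects agrees with it. Section 5.6 gives "Treatment Group 1 (approximately 130 subjects") and about 70 for placebo, which also adds to 200. Section 4 treats a subject as enrolled at randomisation, so 190 and 200 describe the same quantity.

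The planned primary analysis in Section 11.6.1 is a Cochran-Mantel-Haenszel (CMH) test stratified by ribavirin treatment and lymphocyte count. The SAP was written after early termination. Its Section 4.1 records 9 subjects randomised, and its Section 12 withdraws the test p-values, confidence intervals and treatment-difference estimates.

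**The concern.** The 90% figure is the protocol's quantitative reason for the size of the trial. Unequal allocation costs efficiency here: the placebo arm has the larger binomial variance (0.21 against 0.09), and 2:1 makes it the smaller arm. A 2:1 design should therefore need clearly more than the roughly 158 subjects of a 1:1 design under the same test, yet the protocol arrives at 160.

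If the figure is wrong, a reader relying on Section 11.2 would believe the type II error was 10% when the stated method implies about 18%. The dropout inflation carries the shortfall into the number randomised. The disagreement between 190 and about 200 then leaves it unclear which size the power statement is meant to justify.

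**Working it through.** **Inputs** (Sections 11.2 and 5.6): placebo rate p1 = 0.30; EDP-938 rate p2 = 0.10, reading the reduction as 20 percentage points; two-sided alpha 0.05 (z = 1.960); 90% power (z = 1.2816); allocation k = 2 EDP-938 per placebo; 15% dropout.

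**1. Required size by the stated method.** For an unpooled z-test,

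n(placebo) = (1.960 + 1.2816)² × [p1(1 − p1) + p2(1 − p2)/k] / (p1 − p2)²

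= 10.507 × (0.21 + 0.09/2) / 0.04 = 10.507 × 0.255 / 0.04 = 66.98.

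This gives 67 placebo + 134 EDP-938 = **201**. The plan's figure of 160 does not reproduce; 201 is about 25% larger.

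**2. Power at 160 by the stated method.** With 53.3 placebo and 106.7 EDP-938,

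SE = √(0.21/53.3 + 0.09/106.7) = 0.0691; 0.20/0.0691 − 1.960 = 0.932; power = Φ(0.932) = **82.4%**.

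**3. Other ways to reach 160.** Totals for 90% power, 30% against 10%, two-sided 0.05 unless noted:

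| Calculation | Total |
|---|---|
| 2:1 unpooled (as stated) | 201 |
| 2:1 pooled | 180 |
| 2:1 pooled, continuity-corrected | 201 |
| 2:1 unpooled, one-sided 0.05 | 165 |
| 1:1 unpooled | 158 (10.507 × 0.30/0.04 = 78.8, so 79 per arm) |
| 1:1 pooled | 164 |
| 2:1 with the larger arm on placebo, unpooled | 156 |

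None of the variants that keep two-sided 0.05 and the stated direction of allocation comes near 160. The 1:1 calculations and the placebo-heavy ratio do.

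**4. Power at 160, 2:1, by type of test.** The exact rows use 107 + 53.

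| Test | Power |
|---|---|
| Unpooled, normal approximation | 82.4% |
| Unpooled, exact binomial | 84.4% |
| Pooled, normal approximation | 86.9% |
| Pooled, exact binomial | 88.0% |

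**5. Dropout step.** 160/0.85 = 188.2, so 190 follows from 160 and this step is sound. For the stated design it should start from 201: 201/0.85 = 236.5, or 237 randomised.

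**6. Power at the stated randomised totals** (unpooled approximation).

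| Randomised | Evaluable after 15% loss | Power after loss | Power with no loss |
|---|---|---|---|
| 190 at 2:1 | 161.5 | 82.8% | 88.3% |
| 200 at 2:1 | 170 | 84.6% | 89.9% |
| 200 as 130 + 70 | 110.5 + 59.5 | 85.9% | 90.8% |

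For 170 at 2:1: SE = √(0.21/56.67 + 0.09/113.33) = 0.0671; 0.20/0.0671 − 1.960 = 1.02; Φ(1.02) is about 85%.

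**The case against.** The strongest reply is that the unpooled z-test is not the analysis. The primary test is a stratified CMH test, whose null variance is closer to a pooled one, and for a pooled test the shortfall at 160 is two to three points rather than eight. At about 200 randomised the case is better still: 130 + 70 meets 90% by the stated test if nobody is lost (90.8%), and after 15% loss (110 + 59) the exact power of an unstratified pooled test is about 90%. This stands. It means that 18% should not be read as the false-negative risk of the planned analysis. It does not rescue Section 11.2, which names the unpooled test, 160 subjects and 90% together; at 160 even the pooled figures stay below 90%.

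Some stronger readings are tempting, but the documents do not support them:

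- A reader might infer that 160 was computed for 1:1 by mistake. It is the closest match among the unpooled calculations, but a placebo-heavy 2:1 ratio (156) also fits and no derivation is given.
- A reader might count three competing totals. The 160 is before dropout and 190 is the same requirement after it, so only 190 and about 200 conflict, by roughly 5%.
- A reader might say that 130 and 70 are not 2:1. Both are marked as approximate, and 133 + 67 rounds to them.
- A reader might take the reduction as relative (30% to 24%). That would need about 2,640 subjects, so the protocol's own numbers show that percentage points were meant. Only the word absolute is missing.

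Finally, the trial has ended. With 9 randomised and only descriptive summaries planned, nothing in the final analysis rests on 160, 190 or 90%. That also stands, and it lowers the urgency.

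**Conclusion.** The power statement in Protocol Section 11.2 and the synopsis is wrong as written. By the stated method 160 evaluable subjects at 2:1 give about 82% power, and 90% needs 201. By a pooled-type test power at 160 is about 87-88%, so the practical shortfall for the planned analysis is smaller, but the claim is still not met. Separately, 190 and about 200 randomised need to be reconciled.

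The conclusion assumes an absolute reduction to 10%, allocation of two EDP-938 to one placebo, and two-sided alpha of 0.05. The 87-88% range uses an unstratified pooled test as a stand-in for the CMH test; the effect of stratification cannot be computed because the documents give no stratum sizes or rates.

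This is a documentation error to correct, of lower priority than in a running trial. It does not show that any reported result is invalid. The remaining risk is that the 90% claim is repeated in the clinical study report or reused to size a later study.

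**What to change.** Restate the sample-size paragraph with an absolute effect, one randomised total, and the evaluable number and power that belong to it. For example:

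> Assuming LRTC rates of 30% on placebo and 10% on EDP-938 (an absolute difference of 20 percentage points), a two-sided alpha of 0.05, an unpooled z-test and 2:1 allocation, [N] randomised subjects with 15% dropout leave [n] evaluable and give about [x]% power.

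The two consistent completions are:

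- 190 randomised (about 127 + 63), about 161 evaluable, about 83% power; or
- 200 randomised (about 133 + 67), 170 evaluable, about 85% power.

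The total and its evaluable number must move together: 200 randomised cannot be paired with 160 evaluable at 15% dropout. Use the chosen total in the synopsis and in Sections 3, 5.6 and 11.2. If the sponsor prefers to quote power for a pooled or CMH test, name that test in the same sentence.

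Since the trial is closed, a short note in the clinical study report is sufficient. The cost is wording and a less favourable stated power. No extra subjects are needed and no analysis changes.
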